- g Archived tissue samples obtained since last treatment may be acceptable per Inclusion Criterion #11. Tissue should be submitted during screening but must be submitted before study drug administration on Cycle 1 Day 1. For subjects in the melanoma primary refractory and relapsed cohorts, fresh baseline tumor tissue is mandatory and confirmed by local pathologist review that sample in fact contains tumor tissue (unless medical monitor approval is received).
- h An optional biopsy can be obtained any time after Cycle 1 Day 14, for safety or with confirmed response or progression. For subjects in the melanoma primary refractory and relapsed cohorts, tumor tissue is mandatory **during Cycle 3 anytime between Days 8 and 15 (Study Days 50 and 57)** and confirmed by local pathologist review that sample in fact contains tumor tissue (unless medical monitor approval is received). If the subject progresses before this timepoint then biopsy should be done at time of progression. Note: If the baseline tumor biopsy was found to be inadequate, the patient should not undergo an on treatment biopsy. Post-progression biopsy can still be optional.
- i Initial tumor imaging will be performed within 28 days before the first dose of study treatment. Scans performed as part of routine clinical management are acceptable for use as the screening scan if they are of diagnostic quality and performed within 28 days before the first dose of study treatment (including PET imaging for subjects with DLBCL).
- j On-study imaging will be performed every 9 weeks (± 5 days) after the first dose of study treatment for the first 2 assessments (Weeks 9 and 18) then every 12 weeks thereafter, should follow calendar days, and should not be adjusted for delays in cycle starts or extension of combination treatment cycle frequencies. The same imaging technique should be used in a subject throughout the study. Per the irRECIST v1.1 used in this Protocol, if imaging shows progressive disease, the imaging assessment should be performed at a minimum of 4 weeks later to confirm progressive disease as described in the Protocol.
- k In subjects who discontinue study drug without confirmed disease progression, a radiological evaluation should be repeated at the time of treatment discontinuation (ie, date of discontinuation ± 4-week window).

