**Table 16: Imaging and Treatment After First Radiographic Evidence of Progressive Disease**

	Clinically Stable		Clinically Unstable	
	Imaging	Treatment	Imaging	Treatment
First radiologic evidence of PD	Repeat imaging at $\geq 4$ weeks to confirm PD	May continue study treatment at the investigator's discretion while awaiting confirmatory scan	Repeat imaging at $\geq 4$ weeks to confirm PD if possible	Discontinue treatment
Repeat scan confirms PD	No additional imaging required	Discontinue treatment	No additional imaging required	N/A
Repeat scan shows SD, PR, or CR	Continue regularly scheduled imaging assessments every 12 weeks	Continue study treatment at the investigator's discretion	Continue regularly scheduled imaging assessments every 12 weeks	May restart study treatment if condition has improved and/or clinically stable per investigator's discretion

In determining whether the tumor burden has increased or decreased, investigators should consider all target lesions as well as nontarget lesions. Subjects who are deemed clinically unstable are not required to have repeat imaging for confirmation. If radiologic progression is confirmed, then the subject will be discontinued from study treatment as specified in the Protocol, and the first radiographic evidence of PD should be the date of progression. If radiologic progression is not confirmed, then the subject should resume/continue study treatment and have their next scan according to the Protocol-specified schedule. If progression is not confirmed and the subject continues on treatment, the next scan that documents disease progression (and is confirmed by a second scan at least 4 weeks later), will be considered the date of disease progression.

NOTE: If a subject with confirmed radiographic progression (ie, 2 scans at least 28 days apart demonstrating progressive disease) is clinically stable or clinically improved, and there is no further increase in the tumor dimensions at the confirmatory scan, an exception may be considered to continue treatment upon consultation with the sponsor. Clinically stable subjects should also have at the confirmatory scan no further increase in the target lesions, no unequivocal increase in nontarget lesions, and no additional new lesions develop (nonworsening PD) to continue study treatment.

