7.3. Analysis of the Primary Efficacy Parameter

7.3.1. Primary Efficacy Analysis

The primary variable for the Phase 2 expansion portion of the study is ORR, which is defined as the proportion of subjects with best overall response (CR or PR) by irRECIST v1.1 for select solid tumors and modified Lugano Classification (Cheson et al 2014) for DLBCL. Subjects' overall response will be evaluated as CR, PR, SD, PD, or not evaluable (NE) at each postbaseline radiological assessment based on changes in target lesions, nontarget lesions, and appearance of new lesions. The best overall response will be determined from response assessments before and including the date of starting new anticancer therapy. If any alternative cancer therapy is taken while on study, any subsequent assessments will be excluded from the best overall response determination.

For subjects with measurable disease at baseline, the irRECIST version 1.1 assessment criteria presented in Table 5 can be used to determine the overall response at a given timepoint based on the target lesion, nontarget lesion, and new lesion assessment.

Target Lesions	Nontarget Lesions	New Lesions	Overall Response
CR	CR	No	CR
CR	Non-CR / Non-PD	No	PR
CR	NE	No	PR
PR	Non-PD or NE	No	PR
SD	Non-PD or NE	No	SD
Not all evaluated	Non-PD	No	NE
PD	Any	Yes or No	PD
Any	PD	Yes or No	PD
Any	Any	Yes	PD

Table 5: irRECIST for Overall Response: Measurable Disease at Baseline

A subject is considered an objective responder as assessed by irRECIST if they have an overall response of CR or PR at any postbaseline visit. The proportion of responders within each treatment group will be estimated with 90% confidence intervals (CIs) by treatment group. Confidence intervals will be calculated based on the Clopper-Pearson method for binomial distributions. Within each treatment group, 1 sample binomial test will be used to test the null hypothesis.

Using irRECIST criteria, a PD needs to be confirmed as follows.

For each PD, if there is a second PD on the first response assessment that was \geq 4 weeks after the PD, then the PD is defined as confirmed, and the date of progression is the date of the first PD. Otherwise the PD is defined as unconfirmed.

If a subject had an unconfirmed PD, and there are no valid response assessments after that PD (not NE or missing), then the PD will be counted as follows:

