7.4.3. Progression-Free Survival

Progression-free survival is defined as the number of days from the date of first dose (which is not necessarily Day 1) to the earlier of death or disease progression by irRECIST v1.1 for selected solid tumors and the modified Lugano Classification for DLBCL. Date of death will be determined using the Death Report, the Survival Follow-Up, and the Subject Status eCRFs. Disease progression is defined as progression confirmed by a second, consecutive assessment at least 4 weeks apart with the option for continuing treatment while awaiting radiologic confirmation of progression. Censoring for PFS will follow the algorithm outlined in Table 6, which is based on FDA guidance (FDA 2007). Note that the Protocol mandates radiological evaluation of subjects every 9 weeks for the first 18 months and then may be done every 12 weeks thereafter. The analyses will be based on the efficacy evaluable population, according to treatment assignment. Time-to-event data will be analyzed by the Kaplan-Meier method.

Situation	Outcome	Date of Progression or Censoring
No baseline tumor assessments	Censored	Treatment start date
Progression documented between scheduled visits	Progressed	 Earliest of: Date of radiological assessment showing new lesion (if progression is based on new lesion); or Date of last radiological assessment of measured lesions (if progression is based on increase in sum of measured lesions)
No progression	Censored	Date of last valid radiologic assessment (not NE and not missing)
Treatment discontinuation for undocumented progression	Censored	Date of last valid radiologic assessment (not NE and not missing)
Treatment discontinuation for toxicity or other reason	Censored	Date of last valid radiologic assessment (not NE and not missing)
New anticancer treatment started	Censored	Date of last valid radiologic assessment (not NE and not missing)
Death before first PD assessment	Progressed	Date of death
Death between adequate assessment visits	Progressed	Date of death
Death or progression after more than 1 missed assessment	Censored	Date of last valid radiologic assessment (not NE and not missing)

Table 6: Evaluation and Censoring of Progression-Free Survival

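### SAP 7.3.1 can date progression 1 to 27 days late when a subject off both drugs has a second PD scan less than 28 days after the first and no later scan

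*Protocol*

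**What the plan says.** **When scans are done.** For subjects who stop study drug without confirmed progression, footnote k of Protocol Table 12 says that "a radiological evaluation should be repeated at the time of treatment discontinuation (ie, date of discontinuation ± 4-week window". For a subject whose imaging shows PD, footnote j of the same table says "the imaging assessment should be performed at a minimum of 4 weeks later to confirm progressive disease". Protocol Tables 10 and 16 repeat the 4-week minimum, and for clinically unstable subjects ask for the repeat only if possible. Section 7.6.3.1 does not require a repeat in unstable subjects. It describes confirmed progression as "2 scans at least 28 days apart demonstrating progressive disease", so 4 weeks means 28 days.

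**How progression is dated in the protocol.** Once radiologic progression is confirmed, Section 7.6.3.1 says "the first radiographic evidence of PD should be the date of progression".

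**How progression is dated in the SAP.** Section 7.3.1 reads "For each PD, if there is a second PD on the first response assessment that was" at least 4 weeks after it, "then the PD is defined as confirmed, and the date of progression is the date of the first PD". Any other PD is unconfirmed. A rescue rule follows, with this opening condition: "If a subject had an unconfirmed PD, and there are no valid response assessments after that PD (not NE or missing". Its first sub-bullet counts such a PD as confirmed, on its own date, if the subject came off both drugs, or left the study, ahead of a later valid assessment. For PFS, Section 7.4.3 adds: "Disease progression is defined as progression confirmed by a second, consecutive assessment at least 4 weeks apart".

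**The concern.** A second scan that agrees with the first should not move the progression date later. Under the literal rule it can. If the second PD comes too soon to confirm the first, its presence still closes the rescue route for the first, because a valid assessment now follows it. The second PD has nothing after it, so it is rescued in its place and supplies the date.

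The pattern can occur in subjects who stop at their first PD because they are clinically unstable. For them the early scan may well be the last: repeat imaging is not mandatory, and Amendment 10 ended disease follow-up after treatment (Protocol Section 6.4.2). Where the pattern occurs, the shift always lengthens PFS, in single-arm cohorts with no concurrent control. PFS by cohort remains a planned output (SAP Appendix E, Tables 2.2.3.1 to 2.2.3.11).

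**Working it through.** The documents state no delay figure, so there is nothing of theirs to reproduce. The check applies the written rule to simple scan histories.

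**Inputs**
- Confirmation interval: 28 days (Protocol 7.6.3.1; SAP 7.3.1).
- Confirmation test: the first assessment at least 28 days after the PD is also PD (SAP 7.3.1).
- Rescue: no valid assessment after that PD and, here, subject off both drugs (SAP 7.3.1).
- Footnote k window: discontinuation day minus 28 to plus 28.

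**1. Literal rule.** Let the first PD be day 0 and the second PD day t, with the subject off both drugs.

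| Scans | First PD confirmed? | First PD rescued? | Progression date |
|---|---|---|---|
| PD at 0 only | no | yes | day 0 |
| PD at 0 and 7 | no (7 < 28) | no (a scan follows) | day 7 |
| PD at 0 and 14 | no | no | day 14 |
| PD at 0 and 27 | no | no | day 27 |
| PD at 0 and 28 | yes | not needed | day 0 |
| PD at 0, 14 and 35 | yes (35 ≥ 28) | not needed | day 0 |
| PD at 0, 14 and 63 | yes (63 ≥ 28) | not needed | day 0 |

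For t = 1 to 27 with no later scan the delay is t days, so at most 27. If t is spread evenly over 1 to 27 (an assumption), the mean is (1 + 27)/2 = 14 days.

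**2. Does footnote k force the early scan?** Suppose treatment stops d days after the first PD, with d from 0 to 28. The window ends on day d + 28, so the days that satisfy both footnote k and the 28-day minimum number (d + 28) − 28 + 1 = d + 1:
- d = 0: 1 day
- d = 7: 8 days
- d = 14: 15 days
- d = 28: 29 days

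The first PD scan, on day 0, also lies inside the window for all these d. As an example, take PD on Day 63 and drugs stopped on Day 64. The window is Day 36 to Day 92, it contains the Day 63 scan, and Days 91 and 92 meet both rules. A Day 77 scan is allowed but not compelled.

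**3. The other reading of the SAP.** In that example the drugs stopped on Day 64, ahead of a Day 77 assessment. Taken alone, the sub-bullet would confirm the Day 63 PD and date it Day 63. The opening condition excludes that PD, because Day 77 follows it. The same record therefore yields Day 63 or Day 77, depending on which clause governs.

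**4. Scale.** Mean PFS shift = share affected × average delay. The share is assumed.
- 5%: 0.05 × 14 = 0.7 days; at most 0.05 × 27 = 1.35 days.
- 30%: 0.30 × 14 = 4.2 days; at most 0.30 × 27 = 8.1 days.

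**The case against.** The strongest reply is that the protocol already steers sites away from this pattern. Footnote j and Tables 10 and 16 time the repeat scan at 4 weeks or more, and an unstable subject need not be rescanned. If those instructions are followed, the subject has no repeat or one at 28 days or later, and both give the first PD date. This stands as to frequency. It does not tell the programmer what to do with an early second PD when one is recorded.

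A reader might infer that the end-of-treatment window conflicts with the 4-week interval. It does not. The two have different anchors, they overlap whenever treatment stops on or after the PD date, and the first PD scan may itself fall inside the window.

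A reader might also infer that the SAP flatly contradicts Protocol 7.6.3.1. That section's first-PD date depends on confirmation, which is absent in this pattern, so the protocol does not expressly date the case.

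Two further points stand. The sub-bullet gives a textual basis for the earlier date, so the late date rests on the literal opening condition. A later PD scan at 28 days or more also restores the first date, because the SAP does not let an early scan block confirmation.

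**Conclusion.** The concern holds in a narrow form. For a subject off both drugs with a PD, a second PD 1 to 27 days later and nothing after it, the literal text of SAP 7.3.1 takes the second date. The same section also contains wording that supports the first date. This is an inconsistent rule as well as a missing detail, and when the literal reading is applied the error runs one way.

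The effect is small on any modest assumption: 0.7 to 4.2 days on mean PFS if 5% to 30% of subjects were affected with an average delay of 14 days. Neither the share nor the timing comes from the documents. It would be tempting to treat the proportion of window days before day 28 as the chance of misdating. That is unsupported, since nothing says when within the window scans are done or that a second one is done at all.

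The exposure is to PFS, and to duration of response and duration of disease control in so far as the confirmation rule supplies their PD date. ORR is untouched, because a subject with CR or PR at any postbaseline visit is a responder whatever the PD date.

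**What to change.** In SAP 7.3.1, state that consecutive PD assessments with no CR, PR or SD between them form one progression, dated at the first PD. Count it as confirmed if a PD follows at 4 weeks or later, or if the subject is off both drugs and every later valid assessment is PD. Refer to this rule from Sections 7.4.2, 7.4.3 and 7.4.4. Reword the rescue rule's opening condition and its first sub-bullet so that they agree. With this change, every history in the pattern (t = 1 to 27) is dated day 0, a delay of 0 instead of t days.

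No change to scan timing is needed. Footnotes j and k of Protocol Table 12 need only be reconciled, so that the text shows how they apply together to a subject who stops with an unconfirmed PD.

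The cost is a sentence in the SAP, the cross-references and a small programming change, with no extra scans. PFS estimates would become slightly less favourable.

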**Table 13: Laboratory Assessments**

**As of Amendment 10, for those subjects remaining on study, procedures are simplified. The Schedule of Assessment tables have been amended, and assessments that are no longer required have been deleted. For subjects who meet Amendment 10 criteria for re-treatment, the following Schedule of Assessments should be followed, except for the screening visit, which does not apply.**

Visit Day (Range)	Screening	Combination, Monotherapy, and Re-Treatment Period a								EOT	Safety Follow-Up
		C1D1	Weekly for 6 Weeks (Phase 1 only)	C2D1	C4D1	C6D1 and C8D1	C12D1 and C16D1	Day 1 All Cycles	Every 9-12 Weeks	Discontinuation	42-49 Days After EOT or Last Dose of INCB024360
Laboratory Assessmentb /Window	Day -28 to Day -1	Day 1	± 3 Days	± 3 Days				± 3 Days	± 14 Days	+ 5 Days	+ 7 Days
Comprehensive serum chemistry	X c	X d		X	X	X	X	X		X	X
LFTs			X e,f	X e	X e	X e	X e	X e		X	X
Hematology with differential	X c	X d		X	X	X	X	X		X	X
Coagulation panel (PT, aPTT, INR)	X e	X d,g								X	
Endocrine function testing	X c	X d						X h		X	X
Tumor-specific history	X i										
PD-L1 Testing (NSCLC)	X j										
CA 125 testing (ovarian cancer only)	X								X k	X	
CA19-9 and CEA (gastric cancer only)	X								X k	X	
AFP tumor marker (HCC only)	X								X k	X	
If anti-HCV positive (HCC only):											
HCV genotype	X										
HCV viral load (HCV RNA)	X	X		X	X	X	X	X		X	

**Table 13: Laboratory Assessments (Continued)**

Visit Day (Range)	Screening	Combination, Monotherapy, and Re-Treatment Period a								EOT	Safety Follow-Up
		C1D1	Weekly for 6 Weeks (Phase 1 only)	C2D1	C4D1	C6D1 and C8D1	C12D1 and C16D1	Day 1 All Cycles	Every 9-12 Weeks	Discontinuation	42-49 Days After EOT or Last Dose of INCB024360
Laboratory Assessment b /Window	Day -28 to Day -1	Day 1	± 3 Days	± 3 Days				± 3 Days	± 14 Days	+ 5 Days	+ 7 Days
If (1) HbsAg+ or (2) anti-HBc+, anti-HBs-, HbsAg-, and viral load < 100 IU/mL (HCC only):											
Anti-HDV	X										
Anti-Hbe and HbeAg	X										
HbsAg and HBV viral load (HBV DNA)		X		X	X	X	X	X		X	
Anti-HBc (total), anti-Hbe, anti-HBs, and HbeAg								X		X	
Serum pregnancy test or urine	X l										
Serology	X										
Urinalysis	X							X			X

a If subjects are re-treated with MK-3475 as described in Section 6.2.1, subjects should follow this schedule of events.

b All laboratory analysis will be done locally unless otherwise noted.

c If screening laboratory testing occurs within 7 days of Cycle 1 Day 1, it is not required to be evaluated on Day 1 before treatment initiation. See required list of analytes for each panel in Table 14.

d Cycle 1 Day 1 laboratory tests (eg, serum chemistry, complete blood count, and coagulation panel) may be omitted IF the screening test was performed no more than 7 days prior.

e If LFTs are abnormal, then LFT should be monitored closely per standard of care until resolved to baseline.

f LFT testing is required weekly for the first 6 weeks during Phase 1 dose escalation. For Phase 2, weekly LFTs are not required and should be performed on Day 1 of each cycle.

g If a coumarin-based anticoagulant is given, monitor INR weekly for the first 4 weeks after initiation of therapy and upon discontinuation of INCB024360.

h To be repeated every 4 cycles (eg, Cycle 5 Day 1, Cycle 9 Day 1, Cycle 13 Day 1, Cycle 17 Day 1, etc).

i For subjects with SCCHN, HPV status; for NSCLC, EGFR status; for CRC, MSI status; for RCC, MSKCC score; for melanoma, BRAF status; for gastric cancer: CA19-9, EBV, *H. pylori*, CEA; for HCC, AFP, HCV/HBV status.

j PD-L1 testing for subjects with NSCLC may be performed locally using the PD-L1 IHC 22C3 pharmDX assay only. If local test results are unavailable, then tissue must be submitted for central testing before enrollment to determine appropriate cohort.

k Tumor markers should be performed every 9 weeks for the first 2 assessments (Weeks 9 and 18), then every 12 weeks thereafter.

l For women of child-bearing potential, a serum pregnancy test is required at screening but must be within 72 hours before first dose of study treatment. Pregnancy tests (serum or urine) should be repeated if required by local regulations.

**Table 14: Laboratory Tests: Required Analytes**

Serum Chemistry	Hematology	Other
Albumin Alkaline phosphatase ALT AST Amylase Bicarbonate Blood urea nitrogen Calcium Chloride Creatinine Glucose Iron Lactate dehydrogenase Phosphorus Potassium Serum or plasma lipase Sodium Total bilirubin Direct bilirubin (If total bilirubin is elevated above ULN) Total protein Uric acid IgG a	Complete blood count, including: 
 
• Hemoglobin
 
• Hematocrit
 
• Platelet count
 
• Red blood cell count
 
• Reticulocyte count
 
• White blood cell count
 
 Differential count, including: 
 
• Basophils
 
• Eosinophils
 
• Lymphocytes
 
• Monocytes
 
• Neutrophils
 
	Serology: Hepatitis B surface antigen Hepatitis B surface antigen antibody Hepatitis B core antibody Hepatitis C virus antibody HCV-RNA HBV-DNA
		Pregnancy test: Female subjects of childbearing potential only require a serum test at screening. Pregnancy tests (serum or urine) should be repeated if required by local regulations.
		Urinalysis with microscopic examination: Color and appearance pH and specific gravity Bilirubin Glucose Ketones Leukocytes Nitrite Occult blood Protein Urobilinogen
		Coagulation: PT aPTT INR
		Tumor Specific: Ovarian: CA 125 testing Gastric: CEA HCC: AFP HCC (if anti-HCV positive only): HCV genotype, HCV viral load (HCV RNA) HCC (if HbsAg+ or anti-HBc+, anti-HBs-, HbsAg- and viral load < 100 UI/mL): Anti-HDV, anti-Hbe, HbsAg, HBV viral load (HBV DNA), anti-HBc (total), anti-HBs, and HbeAg
	Standard LFT Monitoring	Endocrine Monitoring
	Alkaline phosphatase ALT AST Total bilirubin	ACTH Serum cortisol (9 AM) b LH c Prolactin TSH Free thyroxine (T4) Total triiodothyronine (T3) Serum testosterone (9 AM) b d

ACTH = adrenocorticotrophic hormone; HDL = high-density lipoprotein; HS-CRP = high-sensitivity C-reactive protein;  
 LDL = low-density lipoprotein; LH = luteinizing hormone; PEF = peak expiratory flow; TSH = thyroid-stimulating hormone;  
 VA = alveolar volume.

a Total IgG is obtained by an automated assay such as rate nephelometry. As long as the IgG is measured and not total immunoglobulin, institutional normal method of assessment is acceptable

b Serum cortisol and testosterone ideally should be drawn close to 9 AM but can be done any time before noon.

c Not needed in subjects receiving testosterone therapy.

d Not needed in women, surgically castrated men, or men taking LHRH agonist therapy.

